5 STUDY DESIGN

5.1 Study description

This is an OLE study that will assess the safety, tolerability, and change in focal-onset seizure frequency associated with long-term oral PSL as an adjunctive therapy in adult subjects with drug-resistant epilepsy. This study will enroll consenting subjects, or subjects whose legal representatives have given consent, and who have completed a PSL parent study (eg, EP0091 or subsequent PSL studies).

At the Entry Visit (same day as the end of Conversion Period Visit in the parent study), subjects will sign a written Informed Consent form (ICF) prior to the conduct of any study-related procedure or pre-treatment assessments, and the subject's eligibility will be determined on the basis of the inclusion/exclusion criteria by the Investigator. Eligible subjects must be educated to record all types of seizures that occur in their seizure diary and to complete their diary entries after each seizure or at least once a day. A caregiver is allowed to help the subject with the completion of the subject diary.

Evaluation Period

After the Entry Visit (Visit 1), subjects will return to the clinic for visits as follows:

- Every 2 weeks during Month 1
- Every month during Month 2 and Month 3
- Every 3 months after Month 3 to the end of Year 2

Dose adjustment of PSL and/or concomitant AEDs and/or settings to neurostimulation devices is allowed at any time during the study, if seizure control is insufficient, or in case of safety or tolerability issue. Concomitant AED(s) may be tapered and discontinued to achieve PSL monotherapy, if clinically appropriate in which case the UCB Physician or delegate must be contacted to discuss with the Investigator. New concomitant AEDs, as allowed per protocol (see [Section 7.8.1](#)), may be introduced to optimize seizure control. Subjects who are not able to tolerate or who do not benefit from the PSL treatment may be tapered off PSL and withdrawn from the study.

Taper Period

Subjects who complete the study or who discontinue early will return for an End-of-Study Visit or EDV, respectively, and will be progressively tapered off over 4 weeks and return to the site 1 week after the last PSL intake for an end of Taper Visit. If a subject transfers into either a Managed Access Program or another PSL study, or takes commercially available PSL, the Taper Period may be skipped and the subject may continue treatment without tapering.

Safety Follow-up Period

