- ^g Full physical examination will include assessment of cardiac and respiratory function via auscultation and review of the following body systems: general appearance; ear, nose, and throat; eyes; hair and skin; respiratory; cardiovascular; gastrointestinal; musculoskeletal; hepatic; neurological; and mental status. Brief physical examinations will include a review of the following body systems: general appearance (including mental status); skin; respiratory; cardiovascular; gastrointestinal; and hepatic.
- ^h Brief neurological examination will include a general assessment and evaluation of reflexes, muscle strength and coordination and cerebellar function. Full neurological examination will include in addition, evaluation of cranial nerves, motor system (general muscle strength and tone), and sensations in upper/lower extremities.
- ⁱ Personal outcome assessments will be completed at Visit 6 (Month 6) and Visit 11 (Month 21) (for subjects who agree to participate).
- ^j An ECG at the SFU will be performed only if abnormal at the EOS or EDV Visit. All ECG recordings will be performed with the subject resting in supine position for at least 5 minutes.
- ^k Only subjects who do not require tapering of PSL at M24 will have an echocardiogram at M24. All other subjects will have an echocardiogram at the SFU Visit and at 6 months after the last dose of PSL. A repeat echocardiogram will be performed for subjects with a new finding, Grade 2 severity (moderate), or Grade 3 severity (severe) (see [Section 6.3](#)).
- ^l Results of a serum pregnancy test performed during parent study will be used at Visit 1 together with a urine test performed at Visit 1. Urine pregnancy tests will be used at all other visits for female subjects of childbearing potential.
- ^m Seizure counts are collected on the subject's daily record card on a daily basis.
- ⁿ Assessment includes AED history.
- ^o Medication should be presented at each visit for check on compliance.
- ^p PSL will be dispensed at the EOS Visit only to subjects who will be tapered off PSL.
- ^q The study termination assessment at the EOS visit is for subjects who will transfer into either a Managed Access Program or another PSL study.
- ^r The study termination assessment at the SFU Visit is for subjects who withdraw early or who complete the study, but will not be transferred to either a Managed Access Program or another PSL study.

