6.3.1 Potential drug-induced liver injury PSL discontinuation criteria

Subjects with potential drug-induced liver injury (PDILI) must be assessed to determine if PSL must be discontinued. In addition, all concomitant medications and herbal supplements that are not medically necessary should also be discontinued.

The PDILI criteria below require immediate and permanent discontinuation of PSL:

- Subjects with either of the following:
 - ALT or AST $\geq 5xULN$
 - ALT or AST $\geq 3xULN$ and coexisting total bilirubin $\geq 2xULN$

The PDILI criterion below requires immediate discontinuation of PSL:

- Subjects with ALT or AST $\geq 3xULN$ who exhibit temporally associated symptoms of hepatitis or hypersensitivity. Hepatitis symptoms include fatigue, nausea, vomiting, right upper quadrant pain or tenderness. Hypersensitivity symptoms include fever (without clear alternative cause), rash, or eosinophilia (ie, $>5\%$).

The PDILI criterion below allows for subjects to continue on PSL at the discretion of the Investigator.

- Subjects with ALT or AST $\geq 3xULN$ (and $\geq 2x$ Baseline) and $<5xULN$, total bilirubin $<2xULN$, and no eosinophilia (ie, $\leq 5\%$), with no fever, rash, or symptoms of hepatitis (eg, fatigue, nausea, vomiting, right upper quadrant pain or tenderness).

Evaluation of PDILI must be initiated immediately. It consists of the diagnostic testing and continued monitoring (specific tests dependent on laboratory results and corresponding symptoms) and consultation with a local hepatologist. The local hepatologist is the expert usually consulted by the treating physician for assessment and management of potential hepatic disease. This would usually be a hepatologist, but may be a gastroenterologist. Additional investigation and monitoring may be required and adapted based on the diagnosis after the cause of the liver injury/abnormality is confirmed.

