Evaluation of PDILI must be initiated as described in [Section 9.2.1](#). If subjects are unable to comply with the applicable monitoring schedule, PSL must be discontinued immediately. Investigators should attempt to obtain information on subjects in the case of PSL discontinuation to complete the final evaluation. Subjects with PDILI should not be withdrawn from the study until investigation and monitoring are complete. All results of these evaluations and observations, as well as the reason(s) for PSL discontinuation and subject withdrawal (if applicable), must be recorded in the source documents. The eCRF must document the primary reason for PSL discontinuation.

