8.1.7 Early Discontinuation Visit

The following procedures will be performed by all subjects discontinuing the study early:

- Verify withdrawal criteria
- Obtain TSQM-9
- Obtain C-SSRS data since the last visit
- Obtain HADS data
- Obtain QOLIE-31-P data
- Obtain SSG
- Obtain CIWA-B data
- Measure vital signs (pulse rate, systolic BP, diastolic BP, and respiratory rate), in supine position after 5 minutes of rest
- Measure body weight
- Perform brief physical examination (refer to [Section 9.3.4](#) for details)
- Perform brief neurological examination (refer to [Section 9.3.5](#) for details)
- Perform Psychiatric and Mental Status assessment
- Obtain 12-lead ECG
- Collect blood and urine samples for clinical laboratory analyses
- Perform urine pregnancy test (female subjects of childbearing potential only)
- Seizure evaluation (count and type) from subject's daily record card
- Record concomitant medication and procedures
- Record AEs
- Record health-related outcomes and HRU (refer to [Section 10.5](#) for details)
- Dispense PSL for the Taper Period
- Check PSL accountability

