8.1.8 End of Study Visit

The following procedures will be performed by all subjects completing the study:

- Obtain TSQM-9
- Obtain C-SSRS data since the last visit
- Obtain HADS data
- Obtain QOLIE-31-P data

- Obtain SSG
- Obtain CIWA-B data (in case of discontinuation of PSL treatment)
- Measure vital signs (pulse rate, systolic BP, diastolic BP, and respiratory rate), in supine position after 5 minutes of rest
- Measure body weight
- Perform brief physical examination (refer to [Section 9.3.4](#) for details)
- Perform brief neurological examination (refer to [Section 9.3.5](#) for details)
- Perform Psychiatric and Mental Status assessment
- Obtain 12-lead ECG
- Obtain echocardiogram if required. Only subjects who do not require tapering of PSL at M24 will have an echocardiogram at M24. All other subjects will have an echocardiogram at the SFU Visit and at 6 months after the last dose of PSL.
- Collect blood and urine samples for clinical laboratory analyses
- Perform urine pregnancy test (female subjects of childbearing potential only)
- Seizure evaluation (count and type) from subject's daily record card
- Record concomitant medication and procedures
- Record AEs
- Record health-related outcomes and HRU (refer to [Section 10.5](#) for details)
- Dispense PSL to those subjects requiring a Taper Period
- Check PSL accountability
- Study termination (for subjects completing the study and continuing PSL treatment)

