9.2.1.2.1 Padsevonil restart/rechallenge (if applicable)

Rechallenge with a substance potentially causing drug-induced liver injury is dangerous, may be fatal, and must not occur.

Subjects who are immediately discontinued from PSL due to having met certain criteria for PDILI (as described in [Section 6.3.1](#) and [Table 9-3](#)), but for whom an alternative diagnosis is confirmed, can rarely restart PSL. Rechallenge with PSL can occur only if ALL of the following requirements are met:

- The results of additional testing and monitoring described in [Section 9.2.1.3](#) and [Section 9.2.1.4](#) confirm a nondrug-related cause for the abnormal hepatic laboratory parameters and any associated symptoms (ie, a subsequent alternative diagnosis fully explains the hepatic findings).
- No alternative treatment options are available to the subject.
- The subject has shown clear therapeutic benefit from the PSL.
- Subject's ALT or AST elevations do not exceed $\geq 3xULN$.
- Subject's total bilirubin is $< 1.5xULN$.
- Subject has no signs or symptoms of hypersensitivity.
- The rechallenge is approved by the UCB Study Physician, DMC, and a hepatologist. The hepatologist must be external to UCB but may be a member of the DMC. It is recommended that the hepatologist be a local hepatology expert or the hepatologist treating the subject.
- Subject agrees to the Investigator-recommended monitoring plan.

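### Early Discontinuation Visit dispensing and the taper text carry no liver-injury exception, contradict the immediate-stop rules for potential drug-induced liver injury, and no precedence is stated

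*Protocol*

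**What the plan says.** **Dispensing and taper at early discontinuation.** Protocol 8.1.7 opens with "The following procedures will be performed by all subjects discontinuing the study early" and includes "Dispense PSL for the Taper Period". In Table 5-1 the PSL dispensing cell for the EDV is unqualified. Section 5.1 says that subjects who complete or who discontinue early "will be progressively tapered off over 4 weeks". Its only exemption is for those who continue PSL through managed access, another study or commercial supply. Footnote c to Table 5-1 draws the same line.

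**Liver injury.** Section 6.3.1 says "The PDILI criteria below require immediate and permanent discontinuation of PSL" and lists two: ALT or AST at least 5xULN, and ALT or AST at least 3xULN with total bilirubin at least 2xULN. A third criterion, ALT or AST at least 3xULN with associated symptoms of hepatitis or hypersensitivity, requires an immediate stop. A fourth, milder one leaves continuation to the investigator. Section 6.3.1 also says "Subjects with PDILI should not be withdrawn from the study until investigation and monitoring are complete". Section 9.2.1 keeps the stop permanent unless another diagnosis fully accounts for the liver findings. Section 9.2.1.2.1 says "Rechallenge with PSL can occur only if ALL of the following requirements are met". The list has eight items, among them approval by the sponsor's study physician, the DMC and a hepatologist.

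**Places where the protocol does write a condition.** The End of Study (EOS) list in 8.1.8 says "Dispense PSL to those subjects requiring a Taper Period", and Table 5-1 footnote p says "PSL will be dispensed at the EOS Visit only to subjects who will be tapered off PSL". For pregnancy, 9.1.7 gives the choice between stopping at once and tapering at the EDV.

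**The concern.** Two operative instructions apply to the same person. A subject stopped under one of the three immediate-stop PDILI criteria who later leaves the study falls under 6.3.1 and 9.2.1, which say no further PSL unless the rechallenge conditions are met. The same subject falls under 5.1 and 8.1.7, which call for taper supplies to be handed out. A site that followed 8.1.7 to the letter would breach a safety rule that the protocol states in strong terms: it calls rechallenge after possible drug-induced liver injury dangerous and potentially fatal.

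There is also a data consequence. Several analysis definitions and follow-up windows are anchored on the date of last PSL intake, so they depend on which instruction the site took.

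**Working it through.** The check is textual, apart from one line of algebra on exposure. The documents give no figure on this point to reproduce.

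1. **Scope of the dispensing step.** The 8.1.7 list covers all early discontinuers, and its dispensing line has no condition. The EOS line in 8.1.8 does have one, and footnote p is attached to the EOS cell only.

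2. **Search for an exemption.** Sections 5.1, 6.3.1, 7.2, 8.1.7, 8.2.1 and 9.2.1 and the footnotes to Table 5-1 contain no sentence releasing PDILI subjects from EDV dispensing or from the taper, and none ranks the two sets of rules. The emergency wording in 7.2 concerns how fast a dose may change; it does not cancel a dispensing step or address a subject already off PSL.

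3. **Who is caught.** The conflict needs two things: PSL stopped under one of the three immediate-stop criteria, and a later EDV. Section 6.3.1 treats study withdrawal after PDILI as something that may or may not follow. For the symptomatic criterion, Table 9-3 allows the stop to be temporary or permanent. Under the milder criterion PSL may continue.

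4. **Order of events.** Section 6.3.1 puts the PSL stop first, then the work-up, then any withdrawal. If withdrawal goes through an EDV, the subject is already off drug when 8.1.7 calls for taper supplies. Taking them would be a restart, and 8.1.7 does not refer to 9.2.1.2.1. This step is an inference from the sequence; the protocol does not describe it.

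5. **Effect on derived dates, if it happened.** SAP 9.1 defines exposure as last dose minus first dose plus 1. Let the first dose be Day 1 and the PDILI stop Day S, so exposure is S − 1 + 1 = S days. If taper drug starts after W drug-free days and runs T days, the last dose falls on Day S + W + T and exposure becomes S + W + T days. The increase is W + T days, of which W were drug-free. Also affected:
   - the end of the Exposure Period (SAP 3.2.3);
   - the Kaplan-Meier event date for discontinuation, which SAP 10.2.2.11 sets to the last dose, so it moves by the same W + T days;
   - the Safety Follow-up Visit 30 days after last intake (Protocol 8.3.1);
   - the 6-month echocardiogram (Protocol 9.3.3);
   - the 6-month SAE-reporting window (Protocol 9.1.5).

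**The case against.** The best case against is that the specific rule governs the general list. The hepatic rule is mandatory and stated several times. Section 8 presents its visit lists as an outline, and the routine visit lists also say to dispense PSL without condition, although 6.3.1 keeps PDILI subjects in the study off drug. Read that literally, those lines too would order dosing, so the lists are presumably meant to yield to the treatment rules. The EDV line is also limited to the taper, and someone already off PSL has nothing to taper. Section 7.10 has the IRT assign kits with regard to the dose the subject is due as well as the visit schedule, and 9.2.1.1 requires the Medical Monitor to be notified within 24 hours and the case to be discussed as soon as possible.

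These points stand as reasons why inadvertent dispensing is less likely. They do not remove the contradiction. No precedence is written, 5.1 imposes the taper independently of the visit lists, and 7.10 does not refer to 6.3.1. The EOS wording and the pregnancy text show that the protocol states such conditions where its authors had them in mind.

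A reader might infer more: that every subject stopped for PDILI would be given PSL again, or that the protocol directs a restart after weeks off drug. The documents do not support that. Withdrawal is conditional, some stops may be temporary, no interval between stop and EDV is given, and a site may well apply the hepatic rule.

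**Conclusion.** The protocol is wrong as written on this point. Sections 5.1 and 8.1.7 and the EDV dispensing cell conflict with 6.3.1, 9.2.1 with Table 9-3, and 9.2.1.2.1 for a subject stopped under the immediate-stop PDILI criteria who then reaches an EDV. That the texts conflict is certain. That a subject would be re-exposed is only a possibility, and it rests on the withdrawal sequence in 6.3.1 and on a site following the visit list literally.

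The number affected is not given. A reader might apply an assumed liver-injury rate to the roughly 1000 planned subjects, but the documents supply no such rate, and the result would count PDILI stops, not subjects dispensed PSL at an EDV. The SAP also says that subjects who discontinue are tapered (2.3 and 9.5.4.1), but that is description and adds no separate conflict. The early termination recorded in the SAP does not reconcile the protocol text, and the last-dose derivations still depend on what sites did.

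**What to change.** Reconcile 8.1.7, the Table 5-1 EDV dispensing cell and 5.1 with 6.3.1, 9.2.1 with Table 9-3, and 9.2.1.2.1, so that one explicit instruction on EDV dispensing covers subjects whose PSL was stopped for PDILI. The EOS line, footnote p and the pregnancy text in 9.1.7 show that the protocol can state such conditions briefly. Then check that the IRT specification, which is not among the documents, agrees with the reconciled text. Which clinical rule prevails, and its wording, is for the sponsor's medical team.

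The cost is wording in a few places and one check of the IRT specification, with no added visits or subjects. For data already collected, the dispensing dates listed under SAP section 7, read against the liver-injury forms listed under SAP 9.4, would show whether any such subject was dispensed PSL after the stop.

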8.1.8 End of Study Visit

The following procedures will be performed by all subjects completing the study:

- Obtain TSQM-9
- Obtain C-SSRS data since the last visit
- Obtain HADS data
- Obtain QOLIE-31-P data

- Obtain SSG
- Obtain CIWA-B data (in case of discontinuation of PSL treatment)
- Measure vital signs (pulse rate, systolic BP, diastolic BP, and respiratory rate), in supine position after 5 minutes of rest
- Measure body weight
- Perform brief physical examination (refer to [Section 9.3.4](#) for details)
- Perform brief neurological examination (refer to [Section 9.3.5](#) for details)
- Perform Psychiatric and Mental Status assessment
- Obtain 12-lead ECG
- Obtain echocardiogram if required. Only subjects who do not require tapering of PSL at M24 will have an echocardiogram at M24. All other subjects will have an echocardiogram at the SFU Visit and at 6 months after the last dose of PSL.
- Collect blood and urine samples for clinical laboratory analyses
- Perform urine pregnancy test (female subjects of childbearing potential only)
- Seizure evaluation (count and type) from subject's daily record card
- Record concomitant medication and procedures
- Record AEs
- Record health-related outcomes and HRU (refer to [Section 10.5](#) for details)
- Dispense PSL to those subjects requiring a Taper Period
- Check PSL accountability
- Study termination (for subjects completing the study and continuing PSL treatment)

8.2 Taper Period

8.2.1 End of Taper Visit; up to 4 weeks (\pm 1 week) including 1 week of drug free

The following procedures will be performed for subjects discontinuing the study or completing it without continuation of PSL treatment:

- Obtain C-SSRS data since the last visit
- Obtain CIWA-B data
- Measure vital signs (pulse rate, systolic BP, diastolic BP, and respiratory rate), in supine position after 5 minutes of rest
- Perform brief physical examination (refer to [Section 9.3.4](#) for details)
- Perform brief neurological examination
- Perform Psychiatric and Mental Status assessment

- Perform urine pregnancy test (female subjects of childbearing potential only)
- Seizure evaluation (count and type) from subject's daily record card
- Record concomitant medication and procedures
- Record AEs
- Record health-related outcomes and HRU (refer to [Section 10.5](#) for details) with the exception of socio-professional status
- Check PSL accountability

8.3 Safety Follow-up

8.3.1 Safety Follow-up Visit (30 days after the last PSL intake) \pm 1 week

The following procedures will be performed for subjects discontinuing the study or completing it without continuation of PSL treatment:

- Obtain C-SSRS data since the last visit
- Obtain CIWA-B data
- Measure vital signs (pulse rate, systolic BP, diastolic BP, and respiratory rate), in supine position after 5 minutes of rest
- Measure body weight
- Perform brief physical examination (refer to [Section 9.3.4](#) for details)
- Perform brief neurological examination (refer to [Section 9.3.5](#) for details)
- Perform Psychiatric and Mental Status assessment
- Obtain 12-lead ECG
- Obtain echocardiogram
- Seizure evaluation (count and type) from subject's daily record card
- Record concomitant medication and procedures
- Record AEs
- Record health-related outcomes and HRU (refer to [Section 10.5](#) for details) with the exception of socio-professional status
- Call IRT
- End of diary recording
- Study termination

An echocardiogram will be performed 6 months after last PSL intake for all subjects.

8.4 Unscheduled Visit/Telephone Call

At any time, the subject may have an unscheduled study visit/telephone call if the Investigator and/or the subject deem it necessary. An unscheduled visit may be conducted due to safety or

efficacy reasons and appropriate assessments will be conducted in relation to the reason for the visit. All information, including reason for visit/telephone call, any information on AEs, etc., should be collected in the source documents and recorded in the appropriate section of the eCRF.

